#### 1. Introduction

## 1.1 Background Information

Gingivitis is ubiquitous to all populations and is caused by inadequate control of dental plaque. This causal relationship was first demonstrated by Löe et al. (1965) using what is now universally known as the 'experimental gingivitis model'. During a three-week phase of nontoothbrushing and starting from a zero plaque and gingivitis status, plaque accumulated around the gingival margins and gingivitis developed. Removal of plaque by resuming toothbrushing was followed by re-establishment of gingival health, proving there is a direct link between plaque and gingivitis. Gingivitis precedes periodontal disease in the majority of cases, which is when teeth lose bone and are eventually lost. 50% of our population is susceptible to periodontitis which is a debilitating oral condition. Gingivitis is generally assessed by clinical examination of the gingivae looking for visual signs of gingival inflammation such as redness, bleeding and swelling or a combination of these signs (Löe and Silness 1963; Löe 1967; Saxton and van der Ouderaa 1989; Lobene et al 1986). Various indices measuring gingivitis have been described that are based on these clinical signs, but inevitably they are subjective, only semi- quantitative and examiner drift in scoring may occur within the practical limits of a clinical trial assessment (Eaton et al 1997).

With the increased use of technology in the dental arena, there is more scope to be able to record accurate 3D images of the mouth which can be used by dentists as aids in assessment and monitoring of oral health and disease using non-invasive methodologies.

3D scanning with increased accuracy and resolution, means it is now possible to capture a great detail of the oral hard and soft tissue information. These scans are time efficient, easy to record and available for future reference. They currently employed to construct complex dental implant retained prostheses and also to monitor orthodontic treatment and position of teeth with a high degree of accuracy.

The aim of this study is to investigate the accuracy of 3D intra-oral scanner images (3Shape Trios Scanner) to monitor gingival health compared to traditional assessments made with standard clinical assessments and indices of the gingival tissues. In this study, 3D intra-oral images will be captured and graded according to the modified gingival index (MGI) and compared against standard clinically derived MGI assessments, within the same subject. This study also aims to evaluate the sensitivity of the 3D scanner to differentiate between healthy gingivae and gingivitis, as measured by indirect assessment of images (using MGI). Gingival health assessed by gingival colour and texture will be compared between clinical assessment and assessment of captured scans. If the scans correlate to the clinical scores this technique would allow oral healthcare professionals to scan the mouth, with algorithms determining

gingival health and disease, in accordance with the New 2017 Classification of Periodontal Diseases (Caton et al 2018), using a non-invasive methodology.

## 2. Study Objectives

## 2.1 Primary Objective(s)

To compare the accuracy of intra-oral 3D scanner derived assessment of gingival inflammation compared to standard clinically derived direct scoring of clinical inflammation, both using the modified gingival index (MGI).

## 2.2 Secondary Objective(s)

- 1. To evaluate the sensitivity of the intra-oral 3D scanner derived assessment of gingival inflammation to differentiate between healthy gingivae, mild gingivitis, moderate and severe gingivitis (MGI 0, 1, 2, 3, 4).
- 2. To examine inter-examiner variability of scoring clinical gingival health from intra-oral 3D scanner images using MGI.
- 3. To compare colour and textual changes in scanned images against clinically derived MGI scores of gingival healthy and diseased sites

## 3. Study Design

## 3.1 Study Outline

This study is a blind (blind to the clinicians assessing the 3D image scans) single visit study in healthy participants. Sufficient participants aged over 18 years will be recruited to the study to ensure approximately 210 sites within the mouth are scored in total across all participants assessed. The scorable sites will be recorded by the MGI score (0, 1, 2, 3 and 4), Appendix A. The sites for assessment will be the buccal and lingual margin of each scorable tooth with one score provided for the full buccal margin and one MGI score for the full lingual/palatal margin. It is anticipated that up to 100 participants may be recruited.

Following the provision of informed consent, participants will be enrolled on to the study according to the inclusion/exclusion criteria. After enrollment participants will have their upper and lower anterior dental sextants (canine to canine area teeth) assessed for gingival inflammation using the Modified Gingival Index (MGI) by calibrated dental examiner 1. The MGI (0, 1, 2, 3 or 4) will be recorded clinically for scorable teeth in the upper and lower anterior sextants at 2 sites, the gingival unit buccally and lingual/palatally), per tooth. The clinician will also identify 2 sites (gingival units) in the mouth and score colour and texture of the gingival unit, appendix D. Following the clinical assessments, the examiner will use a 3D Intra-oral scanner to scan the mouth of each participant ensuring that all scorable teeth and gingivae are captured, Appendix B. The scanned images are recorded automatically by the scanner and form a pictorial patient report, Appendix C. A copy of this report will be provided to the participants for their own interest. The first and a second calibrated examiner will

evaluate the 3D Intra-oral scan and record the MGI for all scorable teeth in the upper and lower anterior sextants, (buccally and lingual/palatally), about 2 weeks after the initial scan . Two sites identified per volunteer will also be assessed for colour and texture of the gingival unit by these two examiners and the findings will be compared to the clinical MGI scores for a further comparison of health and gingival disease identification, Appendix D.

The images recorded from the 3D scanner will be stored using the participant's unique ID number. The 3D scans will be anonymised and blindly assessed by the two calibrated (MGI) examiners.

## 3.2 Selection of Participants

## i) 3.2.1 Planned number of participants

Sufficient participants in good general health, aged 18 or over, male and female will be accepted onto the study in order to obtain approximately 80 sites with MGI 0, 40 sites with MGI 1, 40 sites with MGI 2, 40 sites with MGI 3 and a minimum of 10 sites with MGI 4 (scorable sites either from the buccal or palatal aspect).

The selection of suitable participants will be made according to the inclusion and exclusion criteria described in the following sections.

#### ii) 3.2.2 Inclusion Criteria

- Be aged 18 years and over, of either gender and in good health.
- Be willing and physically able to undergo all study procedures.
- Be willing and competent (verbally and cognitively) to give written informed consent.
- Have at least 20 natural teeth.

#### iii) 3.2.3 Exclusion Criteria

- Current participation in any other cosmetic trials, any dental clinical trials or clinical trials.
- Obvious signs of untreated caries or significant periodontal disease, which in the opinion of the Study Dentist, will affect either the scientific validity of the study.
- A periodontal pocket depth >4mm in the anterior upper or lower sextants.
- Any participant who, in the judgement of the investigator, should not participate in the study.
- Current orthodontic treatment.
- An immediate employee of the sponsor or the research team conducting the study.
   Employees of the Sponsor or research site not associated with the research team are eligible to participate.

## 3.3 Withdrawal of Participants.

Participants may discontinue from the study at any time without having to give a
reason. In addition, the Principal Investigator (PI) or designee has the right to
withdraw a participant for any reason that is in the best interests of the participant.

## 3.4 Endpoints

#### iv) 3.4.1 Assessment

The following endpoint will be employed:

- Modified Gingival Index (Lobene) (MGI) derived from clinical assessment of gingival or from 3D-representations, Appendices A and B.
- Red colour threshold and gingivae surface texture in a predefined region of interest of the gingivae (Appendix D).

## Assessment of Safety

Adverse events will be monitored throughout the study (section 5).

Soft and hard tissue assessments will be conducted. Any deviation from the screening assessments will be recorded as an adverse event.

#### 3.5 Concomitant medication

Any concomitant medication, including food supplements and prophylactic treatments will be recorded in the case report form (CRF).

## 3.6 Assessments at Study Visit

The assessments to be conducted at the study visit are presented in Table 1.

Assessment	Visit 1
Informed Consent	X
Medical History Collection	X
Oral Soft and Hard Tissue Assessment	X
MGI/Colour/Texture Assessment	X
Intra oral scan of mouth	X
AE Recording	Х
Remuneration	Х

At the start of the study visit participants will be provided with a Participant Information Sheet containing detailed information about this study to read. The potential participant will be given the opportunity to ask any questions they may have with regards to the study. If the participants are willing to take part in this study, they will be asked to sign the Informed Consent form. Once informed consent has been obtained each participant will be assigned a

unique identification number and their eligibility criteria will be reviewed by the study clinician.

Those participants who qualify for entry onto the study will have their gingival health assessed by MGI (see Appendix A) in the upper and lower anterior sextants by examiner 1, and 2 gingival site units scores for colour and texture.

Following MGI assessment, examiner 1 will use the 3Shape scanner to acquire a scan of the oral hard and soft tissues in the upper and lower anterior sextants. The examiner will ensure the scan captures all scorable teeth and gingivae. The scan will be saved using the participants unique identification number. This completes the participant study visit.

Approximately 2 weeks after the last clinical assessment, examiner 1, and a second examiner (examiner 2) will assess the anonymized 3D oral scans for each scorable tooth for each participant using the MGI scoring system and grade the 2 identified sites for colour and texture.

Scoring intra-oral 3D scanner image assessments of gingival health using the modified gingival index (MGI) will be compared to the clinically derived assessments.

## 4. Safety Monitoring

#### 4.1 Adverse Event and Medical Device Incidents

An adverse event (AE) is any untoward medical occurrence in a participant, whether or not related to the study procedures. Adverse events include any occurrence that is new in onset, an exacerbation of a pre-existing condition and clinically significant laboratory values.

An incident is any malfunction or deterioration in the characteristics and/or performance of a device, as well as any inadequacy in the labelling or the instructions for use which, directly or indirectly, might lead to or might have lead to the death of a patient or user or of other persons or to a serious deterioration in their state of health.

#### 4.1.1 Exceptions

The following medical occurrences will not be reported as AEs;

- Pre-treatment Adverse Events; Any medical occurrence that occurs after informed consent, but before any study assessment is considered as medical history and only recorded as an AE if it worsens during the study.
- Pre-existing medical condition; Events that occur with comparable frequency and severity to the participant's baseline condition are reported as medical history, not AEs.

#### 4.1.2 Study Specific Expected Adverse Event

There are no AEs known to be associated with the use of the 3D intra-oral camera and/or procedures in this study.

## 4.2 Reporting of Adverse Events and Incidents

The handling and reporting of AEs has been formally delegated by the University of Bristol, as Sponsor, to UH Bristol.

All SAEs must be reported to the UH Bristol contact ([name]) by investigational staff within 24 hours of their knowledge of the event. The initial SAE report may be incomplete but must provide the minimal information which is the study number, participant number, start date and SAE term.

The investigator will promptly report all incidents occurring with any medical device provided for use in the study within 24 hours. The Sponsor has a legal responsibility to notify appropriate regulatory bodies and other entities about certain safety information relating to medical devices being used in clinical studies. Prompt notification of incidents by the investigator is essential in order to meet legal obligations and ethical responsibility towards the safety of subjects. The investigator, or responsible person according to local requirements, will comply with the applicable local regulatory requirements relating to the reporting of incidents to the ethics committee.

## 5. Statistical Considerations

## 5.1 Sample Size Calculation

The study will recruit sufficient consenting adult healthy participants (up to 100 if required) who satisfy the eligibility criteria listed in section 3.2. The primary objective to compare scoring clinical gingival health versus scoring intra-oral 3D scanner images of gingival health using the modified gingival index (MGI), to differentiate between healthy gingivae, mild gingivitis (MGI 1 and 2) and moderate to severe gingivitis (MGI 3 and 4). One of the secondary objectives is to examine inter-examiner variability of scoring clinical gingival health from intra-oral 3D scanner images using the modified gingival index.

## 5.2 Definition of Analysis Population

Participant data will be used except where a participant has been significantly non-compliant with the protocol.

#### 5.3 Statistical Methods

MGI scores recorded by examiner 1 for clinical scoring; and MGI scores recorded by examiner 1 from the scans for the same 210 gingival sites are compared by constructing a crosstabulation, highlighting disagreements between scores indicating healthy gingivae, partial mild gingivitis, mild inflammation of the entire gingival unit, moderate gingivitis and

severe gingivitis (MGI 0, 1, 2, 3 and 4). Disagreement probabilities will then be calculated for disagreements between consecutive scores, with confidence intervals. This process will be repeated with MGI coarsened to a 3-point scale, 0, 1-2 or 3-4. These two models will be compared to determine the degree to which the scanned images enable subtler discrimination between MGI 1 and 2 and between MGI 3 and 4. Both row and column disagreement proportions will be calculated, which are analogous to complements of sensitivity and specificity and positive and negative predictive values.

MGI scores recorded by examiner 1 for clinical scoring; and MGI scores recorded by examiner 2 from the scans are compared in exactly the same way.

MGI scores recorded by examiners 1 and 2 from the scans are compared by constructing a crosstabulation as above. As well as the disagreement probabilities, analyses will also be performed based on MGI as a 0 to 4 scale. Thus a root mean square difference in scores will be calculated, and systematic variation between the two observers assessed by examining the mean difference.

It is possible that for one or more gingival sites the two observers agree on their scores from the scan but disagree with the clinical score. In this event, the relevant scan will be reviewed carefully to try to determine whether the scanning process has introduced some specific artefact leading to this pattern of disagreements. The original 3 scores for that site will be used in the statistical analyses nonetheless.

Additional investigation of the images will be undertaken to explore the sensitivity of the device, including the ability of gingival colour and texture assessment from visual and captured images to distinguish between healthy and diseased sites. Further analyses may be undertaken on these anonymised images to compare healthy and diseased sites.

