## Appendix A – MGI Assessment

The scoring of gingival health will be carried out by two trained dental examiners who have been standardised in the indices. Teeth are examined and scored by one examiner and both will perform the 3D intra-oral scans assessments.

Gingival condition is assessed using the Modified Gingival Index (Lobene, 1986) which is a non-invasive visual evaluation of gingival health. For the clinical assessment each scorable tooth in the upper and lower anterior sextants will be classified as healthy or exhibiting gingivitis on a 5-point scale. For each scorable tooth, 2 gingival unit sites will be assessed and recorded at the gingival margin of the buccal and lingual/palatal surfaces). The 5-point scale is as follows:

- 0 = normal (absence of inflammation)
- 1 = mild inflammation (slight change in colour, little change in texture) of any portion of the gingival unit
- 2 = mild inflammation of the entire gingival unit
- 3 = moderate inflammation (moderate glazing, redness, oedema, and/or hypertrophy) of the gingival unit
- 4 = severe inflammation (marked redness and oedema/hypertrophy, spontaneous bleeding, or ulceration) of the gingival unit.

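### The protocol leaves open whether 210 sites is a recruitment target, the total scored or the analysed set, and full anterior scoring passes 210 after about 9 participants

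*Protocol*

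**What the plan says.** Five parts of the protocol bear on the number of sites.

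- **Section 3.1**, as an aim of recruitment: "ensure approximately 210 sites within the mouth are scored in total across all participants assessed". On the number of people: "It is anticipated that up to 100 participants may be recruited".
- **Section 3.2.1**, as quotas: "approximately 80 sites with MGI 0, 40 sites with MGI 1, 40 sites with MGI 2, 40 sites with MGI 3", plus at least 10 at MGI 4.
- **Sections 3.1 and 3.6 and Appendix A**, on what is scored. Clinically, participants have their "upper and lower anterior dental sextants (canine to canine area teeth) assessed for gingival inflammation", and "For each scorable tooth, 2 gingival unit sites will be assessed and recorded". From the scans, both examiners "record the MGI for all scorable teeth in the upper and lower anterior sextants". Section 3.6 repeats that scan reading covers each scorable tooth of each participant.
- **Section 5.2**, on who is analysed: participants' data are used unless there was significant non-compliance. There is no rule at site level.
- **Section 5.3**, on the main comparison: "MGI scores recorded by examiner 1 from the scans for the same 210 gingival sites are compared". Here the figure stands without any word such as approximately. The examiner 2 comparison and the inter-examiner comparison are both defined by reference back to this one.

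**The concern.** The same number does three jobs that are not compatible: a target to recruit towards, the total number of sites scored, and the set that is analysed. Since every scorable anterior site is scored, the total scored can be 210 only if about 9 to 13 people are enrolled, while the protocol allows up to 100.

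If section 5.3 is followed to the letter, 210 sites have to be taken from a larger set. The quotas are defined by MGI score, so that choice can only come after clinical scoring. Nothing in the protocol requires it to be fixed before the scans are read. Two things are then at stake. The main agreement result depends on an undefined choice of sites, and paired readings that have already been made may go unused, at some cost in precision.

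**Working it through.** **The plan's own figure.** The quotas sum to it: 80 + 40 + 40 + 40 + 10 = 210. Section 5.1 gives no alpha, power, expected disagreement or within-mouth correlation, so 210 cannot be derived in any other way.

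**Sites scored.** Canine to canine is 6 teeth per sextant. With two sextants and two sites per tooth, 6 × 2 × 2 = 24 sites per participant, an upper bound.

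- Participants needed for 210 sites: 210 / 24 = 8.75, so about 9. With only 8 scorable anterior teeth (assumed), 210 / 16 = 13.1.
- At 100 participants: 24 × 100 = 2,400 sites (1,600 with 8 scorable teeth). 210 / 2,400 = 8.75%, or 2.1 sites per participant, and 2,400 − 210 = 2,190 sites would lie outside a 210-site analysis.

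**How large a surplus is likely.** This depends on how common each score is, which the protocol does not give. For the MGI 4 quota alone, sites needed = 10 / prevalence:

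| Assumed MGI 4 prevalence | Sites scored | Participants (÷ 24) |
|---|---|---|
| 5% | 200 | about 8 |
| 2% | 500 | about 21 |
| 1% | 1,000 | about 42 |
| 0.5% | 2,000 | about 83 |

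At 5% this quota creates almost no surplus, because 10 / 210 = 4.8% is its share of the plan. The other quotas can create one in the same way if their scores are scarcer than planned.

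**Precision.** Take one pooled disagreement proportion and the design effect 1 + (m − 1) × ICC, where m is the number of sites per participant and ICC (the within-mouth correlation) is assumed. Effective n = sites / design effect. The 210 sites are assumed to be spread evenly, so m = 210 / 40 = 5.25 or 210 / 100 = 2.1. The interval width ratio is √(effective n for 210 / effective n for all).

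| Participants | ICC | Effective n, all sites | Effective n, 210 sites | Width ratio | Narrower by |
|---|---|---|---|---|---|
| 40 | 0.1 | 960 / 3.3 = 291 | 210 / 1.425 = 147 | 0.71 | 29% |
| 40 | 0.5 | 960 / 12.5 = 76.8 | 210 / 3.125 = 67.2 | 0.94 | 6% |
| 100 | 0.1 | 2,400 / 3.3 = 727 | 210 / 1.11 = 189 | 0.51 | 49% |
| 100 | 0.5 | 2,400 / 12.5 = 192 | 210 / 1.55 = 135 | 0.84 | 16% |

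In points, at an assumed 20% disagreement and 100 participants, the 95% half-width is 2.9 against 5.7 (ICC 0.1) and 5.7 against 6.7 (ICC 0.5).

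**The MGI 4 row.** If recruitment stops when that quota fills, the row holds about 10 sites whichever set is analysed. At 20% disagreement its half-width is about 24.8 points even before clustering. The surplus does not help it.

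**Clustering if all sites are used.** At ICC 0.2 and 24 sites per mouth the design effect is 1 + 23 × 0.2 = 5.6, and √5.6 = 2.4. Intervals that treat sites as independent would be about 2.4 times too narrow. With 210 sites over 100 mouths the factor is √(1 + 1.1 × 0.2) = √1.22 = 1.1.

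**The case against.** The strongest reply is that 210 was only ever a target. Section 3.1 introduces it as an approximate aim, section 3.2.1 uses approximate counts and a minimum for MGI 4, and section 5.2 keeps participants' data by default. On that view section 5.3 simply carries the planning figure forward. This stands as a possible reading. A reader might infer that the protocol throws away more than 90% of its paired scores, and the documents do not support that, because no section says that a scored site is left out. The reply does not rescue section 3.1, where about 210 as the total scored cannot be squared with full anterior scoring of more than about 9 to 13 people.

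A reader might also infer that easy or well-imaged sites will be picked and disagreement understated. That is not supported either. Scans are anonymised and read blind to the clinical scores, and choosing sites on the clinical score alone does not bias the row proportions. Bias would need a choice informed by scan scores or image quality, which no section describes. Section 5.3 also keeps the original scores where both scan readers agree against the clinical score, although this covers one pattern and does not say which sites enter.

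A site-selection rule may sit in an analysis plan that is not shown, so its absence is not the point here. The point is the contradiction within the protocol.

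Two further objections stand in full. The precision gain is for a pooled proportion, which section 5.3 does not name among its estimates. And using all sites changes the score mix, which matters for the column proportions, the root mean square difference and the mean difference.

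**Conclusion.** The point holds as a contradiction about the analysis set. Sections 3.1, 3.2.1, 3.6, 5.2 and 5.3 cannot all be met with 210 as target, total and analysed set once enrolment passes about 9 participants with all anterior teeth. At 100 participants a literal 210-site analysis would use as little as 8.75% of the scored sites. The protocol leaves open which sites those would be and does not require the choice to precede scan reading, so selection is possible but not shown.

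The loss of precision is conditional. It is close to nil if MGI 4 is as common as 5% and the other quotas fill as planned. With a surplus, the gain from using all sites is 6% to 29% (40 participants) or 16% to 49% (100 participants) for a pooled proportion, over an assumed ICC of 0.5 to 0.1. It is negligible for the MGI 4 row. The count of 24 sites per mouth is an upper bound. Prevalence, ICC, the 20% disagreement rate and the even spread of the 210 sites are all assumptions.

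**What to change.** Reword sections 3.1, 3.2.1 and 5.3 so that:

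1. The counts 80/40/40/40/10 are minimum numbers of sites by clinical MGI, used only to decide when recruitment stops, and 210 is no longer described as the total scored.
2. Every site with a clinical score and a paired scan score enters the crosstabulations, with confidence intervals that allow for clustering by participant.
3. Column proportions, the root mean square difference and the mean difference are said to depend on the score mix, and are reported for the observed mix or reweighted to the quota mix.

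If a 210-site set is kept, it should be drawn at random within clinical-MGI strata before the scans are read.

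The cost is wording and slightly more analysis work. No extra readings are needed, because both examiners already score all scorable anterior teeth. The downside is that the column, root mean square and mean-difference results no longer describe the fixed 80/40/40/40/10 composition unless they are reweighted.

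### Section 5.3 puts confidence intervals on 210 pooled gingival sites without treating the participant as a cluster, so intervals that take sites as independent would probably be too narrow

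*Protocol*

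**What the plan says.** Protocol section 3.1 recruits enough participants "to ensure approximately 210 sites within the mouth are scored in total across all participants assessed". Section 3.2.1 splits that total into quotas by score. For the four lower scores it asks for "approximately 80 sites with MGI 0, 40 sites with MGI 1, 40 sites with MGI 2, 40 sites with MGI 3". For the highest score the quota is at least 10. The number of participants is left open, with up to 100 anticipated (sections 3.1 and 5.1).

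Section 3.1 limits scoring to the "upper and lower anterior dental sextants (canine to canine area teeth"), and MGI is recorded "for scorable teeth in the upper and lower anterior sextants at 2 sites" per tooth, one buccal and one lingual or palatal.

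For the primary comparison, section 5.3 says that examiner 1's clinical scores and "MGI scores recorded by examiner 1 from the scans for the same 210 gingival sites are compared by constructing a crosstabulation". It continues: "Disagreement probabilities will then be calculated for disagreements between consecutive scores, with confidence intervals". Row and column disagreement proportions are added. The same process is applied to a 3-point MGI scale and to examiner 2's scan scores, and the two examiners' scan scores are cross-tabulated in the same manner.

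In sections 5.1 to 5.3 the participant appears only in connection with recruitment and exclusion from the analysis. Within-mouth correlation is not mentioned. The interval method and the confidence level are not stated.

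**The concern.** Sites from one mouth share a participant, a visit and that participant's scan. A poor scan, or a mouth whose inflammation is hard to grade, can produce disagreement at several sites together. Section 5.3 itself allows that scanning may introduce an artefact. Positive correlation of disagreement within a mouth is therefore likely, and 210 sites then carry less information than 210 independent observations.

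The site is the unit for both the sample target and the crosstabulation, and nothing brings the participant back in. An analyst who follows section 5.3 as written would most naturally compute simple binomial intervals on site counts. Those intervals are the only stated measure of uncertainty for the primary comparison. If they are too narrow, the scanner's agreement with clinical scoring looks better established than it is.

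**Working it through.** **Inputs from the protocol**
- Sites by quota (section 3.2.1): 80 + 40 + 40 + 40 + 10 = 210. This reproduces the stated total.
- Ceiling per mouth (section 3.1): 6 upper + 6 lower teeth = 12, and 12 × 2 sites = 24.
- Participants: up to 100, with no minimum.

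**Range of cluster sizes.** 210 / 24 = 8.75, so about 9 mouths could supply the whole total. At the other end, 210 / 100 = 2.1 analysed sites per mouth. One hundred mouths could yield up to 2,400 scored sites, and the protocol does not say how 210 would be chosen from them. Cluster size is therefore unknown between these limits.

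**Assumption.** The ICC of disagreement within a mouth is not in the protocol. A range of 0.05 to 0.3 is used.

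**Formulas**, with m = sites per mouth in the denominator concerned:
- Design effect: DE = 1 + (m − 1) × ICC
- Correct width / naive width = √DE
- Actual coverage of a naive 95% interval = 2Φ(1.96/√DE) − 1

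**One overall proportion over 210 sites**

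| Participants | m | DE (ICC 0.05 to 0.3) | Width ratio | Coverage |
|---|---|---|---|---|
| 100 | 2.1 | 1.05 to 1.33 | 1.03 to 1.15 | 94% to 91% |
| 20 | 10.5 | 1.5 to 3.9 | 1.21 to 1.96 | 89% to 68% |
| 9 | 23.3 | 2.1 to 7.7 | 1.46 to 2.78 | 82% to 52% |

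Example for 20 participants and ICC 0.3: DE = 1 + 9.5 × 0.3 = 3.85, √3.85 = 1.96, and coverage = 2Φ(1.00) − 1 ≈ 68%.

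In percentage points, at an assumed 20% disagreement, the naive half-width is 1.96 × √(0.2 × 0.8 / 210) = 5.4. With ICC 0.1 it should be 5.7 for 100 participants and 7.6 for 20.

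**A single 40-site MGI row.** Row proportions have smaller denominators, so fewer sites per mouth enter each one. Spread evenly over 9 mouths, m = 40 / 9 = 4.44:
- ICC 0.05: DE = 1 + 3.44 × 0.05 = 1.17, coverage about 93%
- ICC 0.3: DE = 1 + 3.44 × 0.3 = 2.03, coverage about 83%

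If the same 40 sites came from 4 mouths (m = 10), DE would be 1.45 to 3.7 and coverage about 90% to 69%. With one site per mouth in the row, DE = 1 and nothing changes.

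**The MGI 4 row.** If its 10 sites came from two mouths (m = 5), DE = 1.2 to 2.2, and the effective number of sites is 10 / 1.2 = 8.3 down to 10 / 2.2 = 4.5.

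**Check by simulation** (beta-binomial, assumed 30% disagreement, 20,000 runs, ICC 0.05, 0.1, 0.2 and 0.3):
- 9 mouths × 24 sites: naive Wilson coverage 0.83, 0.73, 0.59 and 0.52
- 20 mouths × 10 sites: 0.89, 0.84, 0.76 and 0.68
- A t interval on participant-level proportions covered 0.93 to 0.95 in all eight settings.

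The formula and the simulation agree.

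**The case against.** The strongest reply is that the protocol never says that sites are independent. It promises confidence intervals and names no method, a site-level table is compatible with participant-clustered intervals, and a statistical analysis plan that is not shown may specify them. A reader might infer that simple binomial intervals are planned. The text does not establish that, and this point does not claim it. What remains is that the protocol itself fixes the site as the unit of both the target and the table, and gives no sign that the participant matters to precision.

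A reader might also infer that every reported interval will be too narrow. That would need positive correlation and more than one site per mouth in the cell concerned, and the protocol establishes neither for every cell. With 100 participants and ICC 0.1, the loss is about 5% in width (coverage 93.7%).

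The 9-participant case is an extreme. It needs nearly all 24 sites from every mouth while five score quotas are filled, in people in good health and without significant periodontal disease. Moreover, the overall design effects do not carry over to the 40- or 80-site rows, where the inflation is smaller unless sites concentrate. These objections limit the size of the problem and leave the problem itself in place.

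Two further limits stand. The same two examiners score every scan, so shared examiners are not a source of within-mouth correlation. No intervals are planned for the mean or root mean square difference, so the point does not extend to those.

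**Conclusion.** The concern holds in a limited form. The protocol sets its sample target and its interval estimates on pooled sites, fixes neither participants nor sites per participant, and does not provide for clustering. Intervals that ignore clustering would probably be too narrow. The shortfall runs from negligible, when many mouths give about two sites each, to serious, when few mouths supply most sites. All figures rest on the assumed ICC of 0.05 to 0.3 and on an even spread of sites over mouths. Uneven spread would make matters worse.

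Severity: should fix. Point estimates of disagreement are unaffected, and the protocol states no test, success threshold or decision rule that turns on interval width.

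**What to change.** In section 5.3, state that confidence intervals for the disagreement probabilities, and any given for row and column proportions, treat the participant as the cluster. Either a bootstrap that resamples participants or a cluster-robust variance with a small-sample correction would serve.

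Report the number of participants behind each MGI row. Present rows supplied by only a few participants, probably MGI 4, descriptively. With one or two contributing mouths, neither the bootstrap nor a robust variance is reliable, so clustering methods cannot rescue such a row.

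The cost is a sentence or two of text and a few lines of code, with no new data. The drawback is that the intervals become wider.
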